4.1.3. Part C, the Booster Dose Phase

Part C, the Booster Dose Phase providing a BD for all eligible participants who chose to receive one, is prompted by interim results of an ongoing Moderna Phase 2a study (mRNA-1273-P201), as described in [Section 4.2](#).

Each study participant will receive a notification letter and will be asked to schedule a BD-1 visit at their study site ([Table 23](#)). Principal Investigators should consider current local public health guidance for administration of COVID-19 vaccines under EUA and marketing authorization (if any) when determining the scheduling priority of participants. At the BD-1 visit, each participant will:

- Be encouraged to remain in the ongoing study,
- Sign a revised ICF that includes both updated safety information relevant to the ongoing study and a BD, and the option to receive a BD,
- Be given the option to receive a BD consisting of a 50 µg dose of mRNA-1273,
- Be counselled about the importance of continuing other public health measures to limit the spread of disease including social distancing, wearing a mask, and hand-washing.

After the BD-1 visit, participants who do not receive a BD will continue with the Part C Supplemental SoE for the BD-2 and BD-3 visits but will not have the BD-1a visit or the safety calls ([Table 23](#)).

Participants who request a BD and are eligible and have no contraindications to further dosing (see [Section 7.1](#)) will have the following study site visits and complete scheduled activities (subject to investigational vaccine availability) according to the Part C Supplemental SoE ([Table 23](#)):

- BD-1 visit: Participants will receive a single 50 µg dose of mRNA-1273.
- BD-1a visit: Optional, and subject to blood sample kit availability, Day 4, 3 days after BD on Day 1.
- BD-2 visit: Day 29, 28 days after the BD on Day 1.
- BD-3 visit: Day 181, 180 days after the BD on Day 1.

The investigator is responsible for conducting all assessments as specified in the Part C Supplemental SoE, according to the schedule. As this Supplemental SoE is intended to occur in addition to the original SoEs ([Table 16](#), [Table 17](#), [Table 18](#), and [Table 19](#)) being followed by all participants in Part B, there is a possibility for study visits to overlap. If visits overlap according to respective visit windows, a single visit may be done with the combined study procedures completed once (refer to [Table 4](#) footnotes for more detailed instructions and exceptions).

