4.4. End of Study Definition

Participants are considered to have completed the study if they complete the final visit at Day 759 (Month 25), 24 months following their receipt of the original second dose of IP (where original refers to the IP received following randomization); if a participant did not receive a second dose of IP, their follow-up will be 25 months after first dose of IP. For participants who enter Part C, if visit BD-3 falls after Day 759 (Month 25), then BD-3 will be the final visit.

The study duration will be approximately 26 months for each participant. This includes a screening period of up to 1 month and a study period of 25 months that includes the first dose of IP on Day 1 and the second dose on Day 29 (Part A). The participant's final scheduled visit will be on Day 759 (Month 25), 24 months after the second dose of IP on Day 29 (Month 1) or 25 months after the first dose if the second dose is missed. For participants who enter Part C, if visit BD-3 falls after Day 759 (Month 25), then BD-3 will be the final visit.

The end of study will be the final participant's final scheduled visit at Day 759 (Month 25) or BD-3, whichever is later.

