8.2. Safety Assessments

Safety assessments will include monitoring and recording of the following for each participant:

- Solicited local and systemic ARs ([Section 8.3.5](#)) that occur during the 7 days following each injection (ie, the day of dosing and 6 subsequent days). Solicited ARs will be recorded daily using eDiaries ([Section 8.2.2](#)) (Part A).
- Unsolicited AEs observed or reported during the 28 days following each injection (ie, the day of injection and 27 subsequent days) (Part A [all participants] and Part C [only those

who receive the BD]). Unsolicited AEs are AEs that are not included in the protocol-defined solicited ARs ([Section 8.3.5](#)).

- AEs leading to discontinuation from dosing and/or study participation from Day 1 through Day 759 or withdrawal from the study.
- MAAEs from Day 1 through Day 759 or withdrawal from the study.
- SAEs from Day 1 through Day 759 or withdrawal from the study.
- AEs of special interest (AESIs; for participants who receive the BD in Part C) from BD-Day 1 through Day 759 or withdrawal from the study.
- Abnormal vital sign measurements.
- Physical examination findings.
- Pregnancy and accompanying outcomes.
- Concomitant medications and non-study vaccinations.

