8.3.7. Recording and Follow-up of an AE and/or SAE

The investigator is responsible for ensuring that all AEs and SAEs are recorded in the eCRF and reported to the Sponsor.

Solicited ARs will be collected from Day 1 through 7 days after each dose (Part A). Other (unsolicited) AEs will be collected from Day 1 through 28 days after each dose in Part A (all participants) and Part C (only those who receive the BD).

Both MAAEs and SAEs will be collected from Day 1 throughout the entire study duration (Day 759 for all participants), as specified in the SoEs ([Table 16](#), [Table 17](#), [Table 18](#), [Table 19](#), [Table 21](#), [Table 22](#), and [Table 23](#)). Any AEs occurring before receipt of IP will be analyzed separately from TEAEs.

At every study site visit or telephone contact, participants will be asked a standard question to elicit any medically related changes, including surveillance for COVID-19 symptoms, in their well-being according to the scripts provided. Participants will also be asked if they have been hospitalized, had any accidents, used any new medications, changed concomitant medication regimens (both prescription and over-the-counter medications), or had any non-study vaccinations.

In addition to participant observations, physical examination findings or other documents relevant to participant safety classified as an AE will be documented on the AE page of the eCRF.

After the initial AE/SAE report, the investigator is required to proactively follow each participant at subsequent visits/contacts. All AEs and SAEs will be treated as medically appropriate and followed until resolution, stabilization, the event is otherwise explained, or the participant is LTFU (as defined in [Section 7.4](#)).

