8.3.8. Time Period and Frequency for Collecting AE and SAE Information

All confirmed serious COVID-19 cases and SAEs will be recorded and reported to the Sponsor or designee immediately and under no circumstance should this exceed 24 hours, as indicated in [Section 8.3.11](#). The investigator will submit any updated serious COVID-19 cases and SAE data to the Sponsor within 24 hours of it being available. COVID-19 cases are defined in [Section 8.1.1](#).

Investigators are not obligated to actively seek AEs or SAEs after conclusion of the study participation (Day 759). However, if an investigator learns of any SAE, including a death, at any time after a participant has been discharged from the study and considers the event to be reasonably related to the study IP or study participation, the investigator must promptly notify the Sponsor.

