 3. Participants with symptoms of COVID-19 will be asked to return within 72 hours or as soon as possible to the study site for an unscheduled visit, to include an NP swab sample (for RT-PCR testing) and other clinical evaluations. If a study site visit is not possible, a home visit may be arranged to collect the NP swab sample and conduct clinical evaluations. If a home visit is not possible, the participant will be asked to submit a saliva sample to the study site by a Sponsor-approved method. At this visit, an NP swab and blood sample will be collected to evaluate for the presence of SARS-CoV-2 infection. An additional NP swab sample will be collected to test for the presence of other respiratory pathogens. In addition, the study site may collect an additional (local/non-central) respiratory sample for SARS-CoV-2 testing to be able to render appropriate medical care for the study participant as determined by local standards of care. Additionally, clinical information will be carefully collected to evaluate the severity of the clinical case.
 4. The eDiary Safety Follow-up prompts will be triggering off of Day 61 to take into consideration the (-3 day) window allowance at Day 29. This first Safety Follow-Up prompt at Day 61 will follow the same 7-day surveillance per protocol.
 5. Trained study personnel will call all participants to collect information relating to any sign/symptoms of COVID-19, MAAEs, AESIs, AEs leading to withdrawal, SAEs, information on concomitant medications associated with those events, and any non-study vaccinations.
 6. All concomitant medications relevant to or for the treatment of an SAE or MAAE will be recorded from Screening through the final visit (Day 759).
 7. One additional ePRO prompt will be sent to participants specifically to solicit the collection of information regarding participant's history of facial injections or dermal fillers, for cosmetic or medical indications such as migraine headaches.

Table 18: Schedule of Events (Surveillance Phase, Day 401 – Day 759)

Visit Number						6
Type of Visit	SC	SC	SC	SC	SC	C
Month (M)/Weekly (W) Timepoint	M15	M17	M19	M21	M23	M25
Study Visit Day	D454 ¹	D514 ¹	D574 ¹	D634 ¹	D694 ¹	D759 ¹ 365 days after Year 1
Window Allowance (Days)	±7	±7	±7	±7	±7	-14/+28
Days Since Most Recent Vaccination						730
Physical examination ²						X
eDiary weekly prompts for surveillance for COVID-19	----Weekly eDiary prompts (Day 401 through Day 759)-----					

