5.1.5. Analysis Periods

Analysis periods and treatment groups for analysis of Part B, Part C, and Primary Series are summarized in Table 1. For effectiveness, participants will be included in treatment groups based on ‘as-planned’ or ‘intent-to-treat’ assignments; for safety, participants will be included in treatment groups based on ‘as treated’ groups (treatment actually received), details are provided to Appendix F. For analysis of immunogenicity, ‘per-protocol’ sets will be used as analysis population and ‘per-protocol’ sets require participants receiving planned treatments.

Table 1 Analysis Periods for Analyses of Part B, Part C, and Primary Series

Treatment Group/Cohort	Description	Analysis Period
Part B (Effectiveness)		
mRNA-1273	Participants randomized to mRNA-1273 in the Blinded Phase Date of reference: PDV/unblinding	From PDV/unblinding to earlier date of (BD-1 visit, DBL or data cutoff date for efficacy, last observed in study ^a)
Placebo	Participants randomized to Placebo in the Blinded Phase and did not request to receive mRNA-1273 in Part B Date of reference: Dose 1 of mRNA-1273	
Placebo-mRNA-1273	Participants randomized to Placebo in the Blinded phase and requested to receive mRNA-1273 in Part B Date of reference: Dose 1 of mRNA-1273 in Part B	
Part B (Safety)		
mRNA-1273	Participants received at least one dose of mRNA-1273 in the Blinded Phase	From PDV/unblinding or 1 st dose of mRNA-1273 in Part B to earlier date of (BD- Day 1, DBL or data cutoff date for safety, last observed in study ^a).
Placebo	Participants only received Placebo in the Blinded Phase and did not receive mRNA-1273 in Part B	
Placebo-mRNA-1273	Participants only received Placebo in the Blinded phase and received mRNA-1273 in Part B	
Part C (Effectiveness, Immunogenicity, Safety)		
Booster 50 µg after mRNA-1273 primary series	Participants randomized to/received mRNA-1273 in the Blinded Phase and received booster 50 µg in Part C Date of reference: date of booster	From dose date in Part C to earlier date of (DBL or data cutoff date for safety, last observed in study ^a).

Booster 50 µg after Placebo-mRNA-1273 Primary Series	Participants randomized to /only received Placebo in the Blinded Phase and received at least one dose of mRNA-1273 in Part B and received booster 50 µg in Part C Date of reference: date of booster	

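### The protocol gives conflicting end dates for safety collection and weekly COVID-19 surveillance when the BD-3 visit falls after Day 759

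*Protocol*

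**What the plan says.** **Text that stops at Day 759**
- Protocol Section 8.2 collects AESIs in booster recipients "from BD-Day 1 through Day 759 or withdrawal from the study". It ends SAEs, MAAEs and AEs leading to discontinuation on the same day.
- Section 8.3.7: "Both MAAEs and SAEs will be collected from Day 1 throughout the entire study duration (Day 759 for all participants".
- Section 8.3.8: "Investigators are not obligated to actively seek AEs or SAEs after conclusion of the study participation (Day 759".
- Table 18: "Weekly eDiary prompts (Day 401 through Day 759", in both the COVID-19 row and the safety row. The Table 17 rows also run to Day 759.
- Table 23, footnote 11, which is attached to the MAAE/AESI and SAE rows, equates the final visit with Day 759 when it sets how long concomitant medications are recorded.

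**Text that goes further**
- Section 4.4, for participants entering Part C: "if visit BD-3 falls after Day 759 (Month 25), then BD-3 will be the final visit". The end of study is the later of the two.
- Section 8.3.3 collects AESIs in booster recipients for the rest of the study.
- Protocol Table 1 covers MAAEs and SAEs over the whole study period.
- Section 4.1.1 has weekly contacts to the end of the study.
- Table 23 marks COVID-19 surveillance, MAAE, AESI and SAE recording, and a blood draw at BD-3.
- SAP Part B/C Section 5.3 also runs surveillance to the end of the study.

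**SAP time at risk.** SAP Part B/C Table 1 gives the Part C period as "From dose date in Part C to earlier date of (DBL or data cutoff date for safety, last observed in study". Its footnote defines last observed as the earliest of discontinuation, completion or death. There is no Day 759 limit there or in the Section 5.3.1.1 censoring rule.

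**The concern.** Sections 8.2 and 8.3.3 give different end dates for the same events in the same participants. Sites could follow either one, so post-booster safety data could be collected over different periods at different sites. AESIs are collected only in booster recipients, and the Section 8.2 clause is the one that would cut them off before the planned 180 days.

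For efficacy, the weekly prompts come from Tables 17 and 18. Table 23 runs alongside those tables and has no weekly contact of its own: after the BD-Day 22 call it lists only BD-2 and BD-3. If prompts stop at Day 759, no schedule table lists a contact until BD-3, yet the SAP goes on counting that time. Post-booster COVID-19 could then be under-ascertained while person-time accrues.

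**Working it through.** **1. The plan's own days.** Table 18 places Day 759 at 730 days after Day 29 and 365 days after Day 394: 29 + 730 = 759 and 394 + 365 = 759. Section 4.1.3 gives "BD-3 visit: Day 181, 180 days after the BD on Day 1", that is 1 + 180 = 181. Both reproduce.

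**2. When BD-3 passes Day 759.** Let b be the study day of the booster, counted from the first dose in Part A. Nominal BD-3 is on day b + 180, which exceeds 759 when b > 579. With the ±14-day window of Table 23:
- latest BD-3: b + 194 > 759 when b > 565
- earliest BD-3: b + 166 > 759 when b > 593

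**3. Length of the interval.** Gap = max(0, b + 180 − 759).

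| Booster day b | Nominal BD-3 day | Gap (days) | Gap with ±14 window | Full weeks | Share of 180 days |
|---|---|---|---|---|---|
| 579 | 759 | 0 | 0 to 14 | 0 | 0% |
| 600 | 780 | 21 | 7 to 35 | 3 | 11.7% |
| 620 | 800 | 41 | 27 to 55 | 5 | 22.8% |
| 660 | 840 | 81 | 67 to 95 | 11 | 45.0% |
| 700 | 880 | 121 | 107 to 135 | 17 | 67.2% |

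**4. Visit windows.** The Day 759 visit may be as late as Day 759 + 28 = 787. BD-3 may be as early as b + 166, so the windows can meet when b ≤ 621, and Section 4.1.3 then allows one combined visit. For b = 620 the BD-3 window opens on Day 786. A combined visit closes the gap if Day 759 means that visit. It does not if Day 759 means the calendar day.

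**5. Calendar dates (assumed).** SAP Part B/C Section 5.3.1.2.1 says only that participants randomized to mRNA-1273 were vaccinated from July to December 2020. I assume first-dose dates in that range, for both arms. For a booster on 7 April 2022, the date of Amendment 10:

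| Assumed first dose | Study day of booster | Gap (days) |
|---|---|---|
| 1 Jul 2020 | 646 | 67 |
| 31 Jul 2020 | 616 | 37 |
| 31 Aug 2020 | 585 | 6 |
| 30 Sep 2020 | 555 | 0 |
| 31 Oct 2020 | 524 | 0 |

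Boosters on 10 September 2021 (date of Amendment 9) or 31 December 2021 give no gap for any of these dates.

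**6. The named cutoff.** SAP Part B/C Section 5.3.1.2.1 names April 2022. With a first dose on 1 July 2020, Day 759 is 29 July 2022. No time after Day 759 exists at that cutoff.

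**7. What BD-3 can recover.** A COVID-19 case needs eligible symptoms and a positive RT-PCR within 14 days of each other (SAP Part A Section 6.3.1.1, retained in SAP Part B/C Section 5.3.1.1). Table 23 has serology at BD-3 but no scheduled swab. Section 5.3.1.1 censors a participant found nucleocapsid-positive at a scheduled visit and does not count a COVID-19 case. A symptomatic illness after Day 759 that was never swabbed therefore adds time but no event. If f is the share of person-time after Day 759 and s the proportion of cases still found there, then under a constant hazard the rate falls by about f(1 − s). The documents give neither f nor s.

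**The case against.** The strongest reply is that Day 759 is shorthand for the final visit. Section 8.3.7 itself speaks of the entire study duration and Section 8.3.8 of the end of participation. With Section 4.4 and the other passages, the intent could be collection through BD-3. That is plausible for those two sections. It does not explain Section 8.2, whose AESI item starts at BD-Day 1 and so was written for Part C, yet still stops at Day 759.

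A reader might infer that the interval is unmonitored. The documents do not support that:
- BD-3 records MAAEs, AESIs and SAEs, and Section 8.3.7 requires a standard question at every visit.
- Table 23 still asks symptomatic participants to come in for a swab.
- Section 8.3.8 still requires notification of a related SAE that the investigator learns of later.
- BD-3 serology feeds the SAP's infection endpoints.

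What lapses, if Table 18 governs, is the scheduled weekly prompt.

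A reader might also infer that post-booster incidence is biased downward. That is possible in analyses after the April 2022 cutoff, but it is not shown. For the relative comparison in SAP Part B/C Section 5.3.1.2.3, participants without a booster also continue to BD-3 (protocol Section 4.1.3). Lapsed prompts could affect both groups, so the direction is not established. The window argument also stands for boosters up to Day 621.

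**Conclusion.** The point holds as an internal contradiction about when safety collection and weekly surveillance end for participants whose BD-3 falls after Day 759. It concerns boosters given after about study Day 579 (565 to 593 with the BD-3 window). If the Day 759 text governs, the interval is 41 days for a Day 620 booster and 121 for Day 700. Section 8.2 then excludes AESIs and SAEs arising in it, and weekly prompts stop.

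The documents give no distribution of booster days and no last day for boosting, so the number affected and the size of any bias cannot be computed. The calendar examples depend on assumed first-dose dates within July to December 2020. Analyses at the April 2022 cutoff are unaffected. Later ones could under-ascertain COVID-19 after the booster.

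**What to change.** - **Protocol.** Reconcile Sections 8.2, 8.3.7 and 8.3.8, the eDiary rows of Tables 17 and 18, and Table 23 footnote 11 with Sections 4.1.1, 4.4 and 8.3.3, protocol Table 1 and the BD-3 column of Table 23. State one end date for AESI, SAE and MAAE collection and for weekly prompts in Part C participants, consistent with the end-of-study definition in Section 4.4. Say whether Day 759 means the visit or the calendar day.
- **SAP Part B/C.** Align the end of Part C time at risk in Table 1 and Section 5.3.1.1 with the end of active COVID-19 surveillance. If weekly surveillance is confirmed through BD-3, no separate SAP change is needed.

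The cost is a wording change and, if surveillance is confirmed through BD-3, eDiary prompts kept on for some further weeks in participants with a late BD-3. The SAP edit needs no new data.

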8.2.1. Safety Phone Calls

A safety phone call is a telephone call made to the participant by medically qualified study staff. Medically qualified staff are those appropriately delegated individuals who are permitted to elicit verbal medical history from participants based on local regulations and local licensing requirements.

This call will follow a script, which will facilitate the collection of relevant safety information. The participant will be interviewed according to the script about occurrence of unsolicited AEs, MAAEs, SAEs, or AEs leading to study withdrawal and concomitant medications associated with those events, receipt of any non-study vaccinations, and pregnancy. Occurrence of AEs will only be collected by safety phone call during the Vaccination Phase ([Table 16](#), [Table 21](#), and [Table 23](#)).

The timing of the safety phone calls and the relevant safety information collected is provided in the SoEs ([Section 11.1](#)).

All safety information described by the participant must be documented in source documents and not documented on the script used for the safety telephone contact. All AEs, MAAEs, SAEs, and AEs leading to study withdrawal must be recorded in the eCRF as specified in [Section 8.3.7](#).

8.2.2. Use of Electronic Diaries

In Part A, the Blinded Phase of the study, at the time of consent, the participants must confirm they will be willing to complete an eDiary (for 7-day reactogenicity and to surveil weekly for COVID-19 symptoms) using either an application downloaded to their smartphone or using a

device that is provided at the time of enrollment. This study will utilize the Medidata Patient Cloud Application as the eDiary for both collection of 7-day reactogenicity and weekly eDiary prompts to elicit an unscheduled Illness Visit if the participant is experiencing COVID-19 symptoms. This application allows for real-time data collection on a 21 CFR Part 11 compliant system directly from participants.

In Part A, the Blinded Phase of the study, before enrollment on Day 1, the participant will be instructed to download the eDiary application on their personal smartphone or will be provided a Sponsor-provisioned device to record solicited ARs ([Section 8.3.5](#)) and also to be utilized for eDiary prompts through the COVID-19 surveillance period.

In Part A, the Blinded Phase of the study, at each dosing visit, participants will record data into the eDiary starting approximately 30 minutes after dosing under supervision of the study site staff to ensure successful entry of assessments. The 30-minute assessment is an opportunity for site staff to train the participant. The site staff will perform any retraining as necessary. Study participants will continue to record data in an eDiary after they leave the study site, preferably in the evening and at the same time each day, on the day of dosing and for 6 days following dosing.

In Part A, the Blinded Phase of the study, the following local ARs will be solicited by the eDiary: pain at injection site, erythema (redness) at injection site, swelling/induration (hardness) at injection site, and localized axillary swelling or tenderness ipsilateral to the injection arm. The following systemic ARs will be solicited by the eDiary: headache, fatigue, myalgia (muscle aches all over the body), arthralgia (aching in several joints), nausea/vomiting, body temperature (potentially fever), and chills.

In Part A, the Blinded Phase of the study, solicited local and systemic reactogenicity ARs, as defined in [Section 8.3.5](#), will be collected on the day of each IP injection and during the 7 days after IP injection (ie, the day of dosing and 6 subsequent days). Any solicited AR that is ongoing beyond Day 7 will be reported in an eDiary until resolution. Adverse reactions recorded in diaries beyond Day 7 should be reviewed by study site staff either during the next scheduled phone call or at the next study site visit ([Table 16](#)).

If eDiary prompts result in identification of relevant safety events according to the study period or symptoms of COVID-19, a follow-up safety call will be triggered.

In Part A, the Blinded Phase of the study, at each dosing visit, participants will be instructed or reminded on thermometer usage to measure body temperature, ruler usage to measure injection site erythema and swelling/induration (hardness), and self-assessment for localized axillary swelling or tenderness on the same side as the injection arm.

In Part A, the Blinded Phase of the study, daily oral body temperature measurement should be performed at approximately the same time each day using the thermometer provided by the study site.

Surveillance for signs and symptoms of COVID-19 will start at Part A Day 1 and continue weekly through the entire Surveillance Phase of the study ([Table 17](#) and [Table 18](#)). After participants complete Part A Vaccination Phase of the Study ([Table 16](#) and [Table 21](#)), the weekly eDiary Safety Follow-up prompts will be triggered on Day 61 ([Table 17](#)). The weekly eDiary prompts will utilize the same Medidata Patient Cloud Application. Each week (ie, every 7 days) the participant will receive a prompt on their smartphone device to regularly surveil for signs and symptoms of COVID-19 and any other changes in health status. The participant will be trained on how to complete the weekly eDiary prompts at the Part A Day 57 clinic visit and also reminded to call the site immediately if they experience any COVID-19 symptoms. The weekly eDiary prompt will inquire about the following:

- Changes in health since the last time completing the weekly eDiary prompt or the last contact with the study staff
- Any known exposure to someone with SARS-CoV-2 infection or COVID-19 since the last time completing the weekly eDiary prompt or the last contact with the study staff
- Capture of any COVID-19 symptoms currently being experienced or experienced since the last time completing the weekly check-in as defined in [Section 8.1.2](#)
- Any contact with a healthcare provider that may indicate an MAAE.

A positive response by the participant to these prompts will result in a notification to both the participant and study staff to arrange a call. A follow-up safety call will be performed to the participant to determine if an unscheduled Illness Visit for the participant should be arranged as defined in [Section 8.1.2](#). The results of the safety call should be recorded in the appropriate source documentation.

If a participant does not respond to the weekly eDiary within a 2-day window around the scheduled timepoint, study staff will follow up directly with the participant via phone call or text to confirm their health status and to remind the participant of the importance of maintaining weekly contact via the eDiary prompt.

In addition, there will be an eDiary prompt to solicit the collection of information regarding participant's history of facial injections or dermal fillers, for cosmetic or medical indications such as migraine headaches.

